### Assessment of Intensity

For all unsolicited AEs not represented in the toxicity scale for Laboratory Values ([Section 16.1; Appendix I: Toxicity Scale for Laboratory Values](#)), the maximum intensity will be based on the following descriptions:

- Grade 1     An AE which is easily tolerated by the subject, causing minimal discomfort and not interfering with daily activities.
- Grade 2     An AE which is sufficiently discomforting to interfere with daily activities.
- Grade 3     An AE which prevents daily activities. (Such an AE would, for example, prevent attendance at work and would necessitate the administration of corrective therapy.)

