### Assessment of Causality

The relationship between the occurrence of an AE and the IMP will be assessed using the categories presented below. For expedited reporting and all other purposes, the categories “none” and “unlikely” will represent no evidence or argument to suggest a causal relationship, while “possible”, “probable” and “definite” will be seen to convey that there is evidence or argument to suggest a causal relationship. Following worst case scenario all AEs without a causality assessment from the investigator will be classified as “possible”.

---

None	The time interval between the administration of the IMP and the occurrence or worsening of the AE rules out a relationship, and/or  another cause is established and there is no evidence of a (concomitant) causal connection with or worsening caused by the IMP.
Unlikely	The time interval between administration of the IMP and the occurrence or worsening of the AE makes a causal relationship unlikely, and/or  the known effects of the IMP or substance class provide no indication of a (concomitant) causal connection with or worsening caused by the IMP and there is another cause which serves as an adequate explanation, and/or  although the known effects of the IMP or substance class make it possible to derive a plausible causal chain with regard to a (concomitant) causal connection or worsening, however, another cause is considerably more likely, and/or  another cause of the AE has been identified and a (concomitant) causal connection with or worsening caused by the IMP is unlikely.

---

---

Possible	
A plausible causal chain with regard to a (concomitant) causal connection with / worsening of the AE can be derived from the pharmacological properties of the IMP or substance class. However, other approximately equally likely causes are known, or
 
although the pharmacological properties of the IMP or substance class provide no indication of a (concomitant) causal connection with / worsening of the AE, there is no other known cause which provides an adequate explanation.

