### Treatment Emergent Adverse Event

An adverse event (AE) with onset either on the day of a vaccination, but after injection, or within the 28 days following injection. AEs recorded outside the 28 day window after the last injection of trial vaccine will be classified as non-treatment emergent AEs.

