### Pre-treatment Adverse Events

AEs recorded after the signing of the informed consent form but before the first injection of trial vaccine are considered pre-treatment AEs.

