### Non-treatment Emergent Adverse Events

Events recorded in the active trial phase but not in the treatment phase. New non-serious or non-special interest AEs according to protocol will not be recorded in the FU phase. However, should any such events be recorded they will also be considered as non-treatment emergent. The classification of AEs into treatment emergent or non-treatment emergent will be decided based on the onset date/time of the AE.

Note that all Serious Adverse Events (SAEs) and Adverse Events of Special Interest (AESIs) within the active and FU phases are considered treatment emergent. SAEs and AESIs within the screening phase are considered non-treatment emergent.

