### 3.3.2 Assignment of AEs to Vaccination Period

Each AE will be assigned to a vaccination period using date/time of vaccination and date/time of the start of the AE.

If start time is missing and start date of AE coincides with the date of a vaccination, the AE will be assigned to the vaccination period corresponding to the vaccination on this date.

Each AE starting at or after any vaccination not matching the definition of a solicited AE is defined as an unsolicited AE. If a solicited AE begins outside of the 8-day window following the previous vaccination it will be considered an unsolicited AE regardless of the preferred term. If start time is missing and start date coincides with date of any vaccination, it will be regarded as a treatment emergent adverse event (TEAE). If the start date is (partially) missing the AE will be regarded as a TEAE following the worst case principle.

If the AE cannot be assigned to a vaccination period because of a (partially) missing start date then it will be assigned to the overall vaccination period. Hence it is possible for the overall vaccination period to include more events than the sum of the individual vaccination periods.

AEs with onset after the active trial phase will be considered to fall within the FU phase. AEs with onset after the active trial phase but at or before the FU 1 visit will belong to FU 1 period. AEs with onset date after FU 1 but before FU 2 visit will belong to the FU 2 period.

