#### Unsolicited AEs

Treatment emergent unsolicited AEs will be summarized by SOC and PT and vaccination period and by subject.

A summary of the number of AEs by intensity and by relationship to trial vaccination will also be presented.

The number of AEs with a reasonable possibility of being related to the vaccine will be presented in a separate listing and summarized in a table by SOC and PT and vaccination period and by subject.

Non-treatment emergent AEs will only be flagged and included in the listing, but will not be included in the tables.

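### For non-serious, non-AESI unsolicited AEs, treatment-emergent status and vaccination period follow onset alone, so a worsening after an injection can go untabulated or be credited to the earlier dose

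*SAP*

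**What the plan says.** The SAP General Definitions describe a TEAE as "An adverse event (AE) with onset either on the day of a vaccination, but after injection, or within the 28 days following injection", and the treatment-emergent ADR definition uses the same onset window. Under Non-treatment Emergent Adverse Events the rule is explicit: "The classification of AEs into treatment emergent or non-treatment emergent will be decided based on the onset date/time of the AE". Anything that starts before the first injection is set apart: "AEs recorded after the signing of the informed consent form but before the first injection of trial vaccine are considered pre-treatment AEs".

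SAP 3.3.2 applies the same logic to dose attribution: "Each AE will be assigned to a vaccination period using date/time of vaccination and date/time of the start of the AE". It also limits the unsolicited category: "Each AE starting at or after any vaccination not matching the definition of a solicited AE is defined as an unsolicited AE".

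SAP 3.5.9 excludes onsets more than 28 days after the previous vaccination from the summary tables and says of unsolicited events: "Non-treatment emergent AEs will only be flagged and included in the listing, but will not be included in the tables". No SAP section mentions worsening or an increase in grade.

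Protocol 8.2.5 grades each unsolicited AE by its worst level ("the maximum intensity will be based on the following descriptions"), and its causality categories cover a worsening as well as a first occurrence. The category None, for example, applies where "The time interval between the administration of the IMP and the occurrence or worsening of the AE rules out a relationship". SAP 3.6 declares no departures from the protocol.

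**The concern.** An investigator can judge that the vaccine made an existing AE worse, yet the SAP has nowhere to count that judgement if the AE began outside a 28-day window. If it began inside an earlier window, the SAP counts it against the earlier dose.

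Two planned outputs are exposed. One is the secondary endpoint on Grade 3 or 4 related AEs within 28 days after each vaccination (SAP 1.4.2), which speaks of occurrence in that interval and not of first onset. The other is the descriptive comparison between vaccination periods in Group 3 (SAP 3.5.9), which bears on whether the booster is tolerated as well as the earlier doses. Group 3 is also the only group with a long uncounted stretch just before an injection.

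**Working it through.** **Plan's own safety figure.** Protocol 9.2 and SAP 3.1 state that 30 subjects per group give at least 95% probability of seeing an AE of incidence 1 in 10. Check: 1 − 0.9^30 = 0.9576, so the figure reproduces. It does not depend on the TEAE definition, but it assumes that every such AE is counted.

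**Uncounted onset windows.** Inputs are the visit windows in Protocol 1.6 (Visit 3 at V1 + 28 to 35 days, Visit 6 at V1 + 84 to 96 days) and the 28-day vaccination period in the SAP General Definitions.

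- Screening: up to 28 days before dose 1, all groups.
- Before dose 2: 28 − 28 = 0 to 35 − 28 = 7 days, all groups.
- Before the booster, Group 3 only: 84 − 35 − 28 = 21 to 96 − 28 − 28 = 40 days.

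SAP Table 1 places the second and third windows outside the treatment phase.

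**Following one AE through the rules.** Take a non-serious unsolicited AE that is not an AESI, is held as a single record, is mild at onset and reaches Grade 3 after the next injection.

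| Onset | Status under the SAP | Per-subject AE tables | Per-vaccination AE tables |
|---|---|---|---|
| Screening | Pre-treatment | Absent | Absent |
| Gap before dose 2 | Non-treatment emergent | Absent | Absent |
| Group 3 gap before booster | Non-treatment emergent | Absent | Absent |
| Within an earlier 28-day period | TEAE | Present at Grade 3 | Grade 3 in the earlier period |

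In the first three rows the event remains in a listing. In the last row nothing is lost per subject; only the dose attribution moves.

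**Does the single-record condition hold?** Protocol 8.1.2 requires changes in health after consent to be entered as AEs. That could lead a site to open a new record for a worsening, and the onset rule would then catch it. Grading by maximum intensity in 8.2.5 points towards one record per event. Neither section settles the matter, so practice may differ among up to 10 sites.

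**Illustration of size.** Let s be the share of affected subjects whose event is left out of the tables. The tabulated detection probability is 1 − (1 − 0.1(1 − s))^30:

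- s = 2%: 0.955
- s = 5%: 0.950 (0.9499 unrounded)
- s = 10%: 0.941
- s = 20%: 0.918

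It falls below 0.95 once s passes about 5%, since 1 − 0.05^(1/30) = 0.0950 and 1 − 0.0950/0.1 = 0.0497. The documents give no value for s, so this shows sensitivity and is not an estimate.

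**The case against.** The strongest reply is that the reach is narrow, and much of it stands.

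- A reader might infer that worsened AEs vanish from every safety table. They do not. SAEs and AESIs in the active and follow-up phases count whatever their day of onset (SAP General Definitions). Laboratory, CD4, vital-sign and ECG summaries do not use AE onset (SAP 3.5.10, 3.5.11). These are not a full substitute, however: the hematology and chemistry shift tables use only below, within and above normal range.
- Solicited AEs are largely protected. A new memory aid is issued after each vaccination (Protocol 8.2.6), and incidence is counted over the 8 days after each one (SAP 3.5.9).
- A reader might infer a bias in one direction throughout. Only the omission from tables is an undercount; an AE carried from one period into the next is moved, not lost. Other rules lean the opposite way: a partly missing start date makes an AE treatment emergent (SAP 3.3.2), and missing causality counts as related (ADR definition).
- Deferral for acute illness (Protocol 4.2.2) and the withdrawal check (4.2.5) reduce the number of AEs ongoing at an injection.
- The safety analysis is descriptive. With 30 subjects per group, the listings can be read case by case.

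The last point softens the consequence but does not answer it: the named endpoint and the between-period comparison would be reported from tables that follow the onset rule.

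**Conclusion.** The point holds for non-serious, non-AESI unsolicited AEs, on condition that a worsening is not entered as a new AE. For these the SAP's rule conflicts with the protocol's causality scale. It leaves some worsened events out of the AE tables and credits others to the earlier dose.

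The size is unknown and probably small. One could assume that 10 to 30% of subjects have an AE ongoing at an injection and that 5 to 20% of those worsen, giving 30 × 0.10 × 0.05 = 0.15 to 30 × 0.30 × 0.20 = 1.8 subjects per group per vaccination. Neither rate is in the documents. The product counts any worsening, includes events that remain TEAEs, and applies no fraction for reaching Grade 3 or being judged related. It therefore does not size the effect on the related Grade 3 or 4 endpoint.

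A reader might also infer that the primary endpoint is compromised. The documents do not support that in general, because SAEs recorded after the first injection count as treatment emergent. One narrow ambiguity remains. SAP 3.5.3 lists SAEs with onset from the first injection, so the place of an AE that begins in screening and becomes serious later is not stated.

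**What to change.** In the SAP definitions of TEAE, non-treatment emergent AE and treatment-emergent ADR, and in 3.3.2, define treatment emergence as onset, or increase in intensity grade, after an injection and within 28 days. Assign a worsening to the vaccination period in which it occurred.

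Instruct sites to enter a worsening after an injection as a new AE record with its own start date and grade.

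For AEs already collected, apply the rule where a dated worsening is available. Otherwise, identify in the listing the AEs that were ongoing at an injection and review them at the data review meeting.

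The cost is SAP wording, related programming and one site instruction. Sample size does not change. TEAE counts may rise slightly. Worsening dates will be incomplete for AEs recorded before the instruction: Protocol Edition 5.0 already refers to a DSMB meeting held during the trial, so the retrospective part can be only partial.

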### **Adverse Drug Reaction**

An Adverse Drug Reaction (ADR) is an AE with either a ‘possible’, ‘probable’, ‘definite’ or missing relationship to the vaccine.

### **Treatment Emergent ADR**

A treatment emergent Adverse Drug Reaction, i.e. an adverse event with either a ‘possible’, ‘probable’, ‘definite’ or missing relationship to the vaccine with onset either on the day of a vaccination, but after injection, or within the 28 days following injection.

### **Treatment Emergent Serious Adverse Event**

All SAEs recorded within the active trial phase (see [Table 1](#)) and FU phase (see [Table 1](#)) are considered as treatment emergent regardless of the day of onset.

### **Treatment Emergent Adverse Events of Special Interest**

Any AESI which is also classified as serious will be included in the analysis of SAEs and will not be included in the analysis of AESIs. All AESIs recorded within the active trial phase (see [Table 1](#)) and FU phase (see [Table 1](#)) are considered as treatment emergent regardless of the day of onset.

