**Table 1 Frequency of Adverse Drug Reactions**

MedDRA* System Organ Class	Very common (≥1/10)	Common (≥1/100 to <1/10)	Uncommon (≥1/1,000 to <1/100)	Rare + (≥1/10,000 to <1/1,000)
Infections and Infestations	-	-	Nasopharyngitis Influenza Upper respiratory tract infection	Sinusitis Conjunctivitis
Blood and Lymphatic System Disorders	-	-	Lymphadenopathy	-
Metabolism and Nutrition Disorders	-	Appetite disorder	-	-
Psychiatric Disorders	-	-	Sleep disorder	-
Nervous System Disorders	Headache	Dizziness	Paraesthesia	Peripheral sensory neuropathy
Ear and Labyrinth Disorders	-	-	Vertigo	-
Cardiac Disorders	-	-	-	Tachycardia
Respiratory, Thoracic and Mediastinal	-	-	Pharyngolaryngeal pain	-

MedDRA* System Organ Class	Very common (≥1/10)	Common (≥1/100 to <1/10)	Uncommon (≥1/1,000 to <1/100)	Rare + (≥1/10,000 to <1/1,000)
Disorders			Rhinitis Cough	
Gastrointestinal Disorders	Nausea	-	Diarrhoea Vomiting Dry mouth Abdominal Pain	-
Skin and Subcutaneous Tissue Disorders	-	-	Rash Pruritus Dermatitis Skin discolouration Ecchymosis Hyperhidrosis Urticaria	Night sweats Angioedema
Musculoskeletal and Connective Tissue Disorders	Myalgia	Pain in extremity Arthralgia	Back pain Neck pain Musculoskeletal stiffness Muscle spasms	Musculoskeletal pain Muscular weakness
General Disorders and Administration Site Conditions	Injection site pain Injection site erythema Injection site induration Injection site swelling Injection site pruritus  Fatigue	Injection site discolouration Injection site nodule Injection site haematoma Injection site warmth Chills Underarm swelling	Injection site irritation Injection site haemorrhage Injection site exfoliation Injection site paraesthesia Injection site inflammation Injection site reaction Injection site rash Injection site movement impairment Application site anesthesia Flushing Axillary pain Chest pain Asthenia Malaise	Oedema peripheral
Investigations	-	Body temperature increased Troponin I increased Pyrexia	Hepatic enzyme increased White blood cell count decreased Mean platelet volume decreased White blood cell count increased	-
Injury, Poisoning and Procedural Complications	-	-	Contusion	-

\* Medical Dictionary for Regulatory Activities (MedDRA)

+ Rare for which 3 events were recorded

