### **9.4.2 Presentation of Data**

For biometrical analysis, data obtained in this trial and documented in the eCRFs will be listed. For parameters of interest, summary tables with descriptive group statistics for metrical variables will be prepared. For categorical / dichotomous variables summary tables showing the absolute and relative count in each category will be prepared.

Full details of the analyses will be defined in the Statistical Analysis Plan (SAP). The SAP will be finalized prior to the respective database lock. The CRO will be responsible for data management and statistical evaluation. Data will be analyzed using SAS®.

Antibody titers and derived parameters, e.g. GMTs and seroconversion rates, will be assessed by vaccinia-specific ELISA and vaccinia-specific PRNT methods as described in [Section 7.1](#).

Clinical laboratory test results will be marked whether the result is below, within or above the respective reference range. The number of values outside of the corresponding reference range will be counted.

All ECGs will be evaluated by a centralized procedure as described in the ECG Assessment Plan. Detailed descriptive analysis of the reasons/category of ECG abnormalities will be performed.

The occurrence of solicited local and general AEs during the 8-day period post vaccination (Days 0–7) will be summarized on a per subject and per vaccination basis.

Unsolicited AEs will be coded using MedDRA coding terminology. The intensity of AEs will be graded according to [Section 8.2](#).

AESIs will be separately listed and tabulated.

SAEs will be listed separately. Each SAE will be described individually in detail.

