#### Safety and Reactogenicity

- Occurrence, relationship to the trial vaccine and intensity of any Adverse Event of Special Interest (AESI).
- Occurrence of any Grade 3 or 4 Adverse Events (AEs) probably, possibly or definitely related to the trial vaccine within 28 days after each vaccination.
- Occurrence, relationship to the trial vaccine and intensity of unsolicited non-serious AEs within 28 days after each vaccination.

- Occurrence, intensity and duration of solicited local AEs (redness, swelling, induration, pruritus and pain) during the 8-day period (day of vaccination and the following seven days) after each vaccination.
- Occurrence, relationship to the trial vaccine, intensity and duration of solicited general AEs (pyrexia, headache, myalgia, nausea, fatigue and chills) during the 8-day period (day of vaccination and the following seven days) after each vaccination.
- Change in CD4 T cell counts in Human Immunodeficiency Virus (HIV)-infected subjects two weeks after each vaccination.

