#### Solicited local AEs reported in the subject memory aid (on days of vaccination and during the following seven days)

- Injection Site Erythema (Redness)

- Injection Site Swelling
- Injection Site Pain
- Injection Site Induration
- Injection Site Pruritus (Itching)

Solicited general AEs reported in the subject memory aid (on days of vaccination and during the following seven days)

- Body Temperature (Fever)
- Headache
- Myalgia (Muscle pain)
- Chills
- Nausea
- Fatigue

Unsolicited AEs reported (on days of vaccination and during the following 28 days)

- Other, unsolicited local and general adverse events following vaccination

SAEs

AESIs

In case an AESI is also an SAE it will be treated and reported as an SAE.

Prior and Concomitant medication

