### 3.5.9 Adverse Events

For the treatment phase analysis a summary table will be presented of the number (and percentage) per vaccination period both per subject and for the number of events for the following events:

- Any AEs
- Any TEAEs
- ADRs (Adverse Drug Reactions)
- Treatment emergent ADRs; note that all local solicited AEs are automatically considered ADRs
- Severe TEAEs (Grade 3 or higher, for grading please refer to the CTP)
- Severe ADRs (ADR graded 3 or higher, for grading please refer to the CTP)
- SAEs
- AESIs
- AEs leading to withdrawal from vaccination
- Deaths

In addition, the incidence of AEs will be calculated (i.e. the number of subjects developing a treatment emergent AE divided by the number of subjects at the time of the vaccination) with corresponding 95% Clopper-Pearson CI. The incidence of any AE will also be calculated for each vaccination period, overall vaccination period and per subject.

For analysis of the treatment phase the information will be based on the data provided from Visit 1 to Visit 5, and additionally Visit 6 to Visit 8 for Group 3.

For the treatment phase, all AEs will be listed by subject, including demographic information, SOC and PT. Any AE with onset later than 28 days after the previous vaccination will not be included in summary tables but will be included in the listing and will be flagged accordingly as non-treatment emergent.

According to the CTP no new AEs should be reported during the FU phase, except SAEs and AESIs, but if any are reported then they will be listed but considered non-treatment emergent.

The number of subjects with at least one treatment emergent AE during the treatment phase will be descriptively compared between the treatment groups, and between vaccination periods within Group 3.

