## 3.6 Alterations in SAP from the Clinical Trial Protocol

None

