- 15.3.1.4.9 Unsolicited Adverse Events: Incidence of Related Adverse Events by Preferred Term and System Organ Class (Per Subject) by Race – FAS
- 15.3.1.4.10 Unsolicited Adverse Events: Incidence of Related Adverse Events by Preferred Term and System Organ Class (Per Subject) by Age Band – FAS
- 15.3.2 Serious Adverse Events/Adverse Events of Special Interest**
- 15.3.2.1 Serious Adverse Events (Per Vaccination Period): Incidence by Preferred Term and System Organ Class – FAS

15.3.2.2 Adverse Events of Special Interest (Per Vaccination Period): Incidence by Preferred Term and System Organ Class – FAS

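### Serious AESIs are taken out of the AESI analysis, so no planned table reports the secondary endpoint of any AESI, and SAP 3.6 does not declare the change

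*SAP*

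**What the plan says.** The secondary safety endpoint reads the same in the protocol synopsis and in SAP 1.4.2: "Occurrence, relationship to the trial vaccine and intensity of any Adverse Event of Special Interest (AESI"). Protocol 8.1.2.3 defines an AESI by cardiac signs or symptoms, clinically significant ECG changes, or troponin I at or above twice the upper limit of normal. Seriousness plays no part in that definition. Protocol 9.4.2 adds, without exception, that "AESIs will be separately listed and tabulated".

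The SAP narrows this in two places:

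- General Definitions, Treatment Emergent Adverse Events of Special Interest: an AESI also "classified as serious will be included in the analysis of SAEs and will not be included in the analysis of AESIs".
- Section 3.4.2, Safety Variables: "In case an AESI is also an SAE it will be treated and reported as an SAE".

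The planned AESI outputs are the AESI row of the overview in SAP 3.5.9, Table 15.3.2.2, Listing 16.2.3.2.2 and the cardiac follow-up Listing 16.2.3.2.3. The SAE counterpart, Table 15.3.2.1, is titled "Serious Adverse Events (Per Vaccination Period): Incidence by Preferred Term and System Organ Class", and no AESI row or flag is planned for it. SAP 3.6, headed "Alterations in SAP from the Clinical Trial Protocol", contains only the entry None.

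**The concern.** The set of events analysed as AESIs is smaller than the set the endpoint names. The output titles say AESIs, not non-serious AESIs, so a reader would take the tabulated incidence as the endpoint and get too low a figure whenever a serious AESI occurs.

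The events removed are also the kind the category was created to capture. Protocol 2.6.1 and section 8 trace the cardiac monitoring to myocarditis and pericarditis seen with earlier smallpox vaccines, and protocol 2.3 cites ten serious cases in one such programme. A comparable serious case here would be absent from the AESI table. SAP 3.5.9 handles AESIs in the same way as SAEs, so the descriptive comparison of AESIs between groups would use the reduced set too.

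**Working it through.** The plan states no figure for AESIs, so there is none to reproduce. The check compares the texts and then shows the effect on the tables.

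**1. Endpoint against analysis rule**

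| Item | Serious AESIs included? |
|---|---|
| Endpoint (protocol synopsis; SAP 1.4.2) | Yes, any AESI |
| AESI definition (protocol 8.1.2.3) | Yes, no seriousness condition |
| Presentation rule (protocol 9.4.2) | Yes, no exception |
| SAP definition of treatment-emergent AESIs | No, removed from the analysis |
| SAP 3.4.2 | No, reported as SAEs |
| SAP 3.6 | No alteration declared |

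The first SAP rule speaks only of analysis. Exclusion from Listing 16.2.3.2.2 follows from SAP 3.4.2, which covers reporting as well.

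**2. Can the any-AESI count be recovered from planned tables?**

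In SAP 3.5.9 "a summary table will be presented of the number (and percentage) per vaccination period both per subject and for the number of events", with SAEs and AESIs as separate rows. Let *a* be the subjects in the AESI row (non-serious only) and *s* those in the SAE row. The number with any AESI is then known only to lie between *a* and *a + s*. It equals *a* if no SAE is an AESI, or if every serious AESI is in a subject already in the AESI row. It equals *a + s* if every SAE subject has a serious AESI and none is in the AESI row. With *a* = 1 and *s* = 2 in a group of 30, the range is 1/30 to 3/30.

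The body-system grouping in Table 15.3.2.1 does not mark AESIs either. Protocol Table 1 puts tachycardia under cardiac disorders, chest pain and peripheral oedema under general disorders, and raised troponin I under investigations ("Body temperature increased Troponin I increased Pyrexia").

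**3. Size in one group of 30**

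Clopper-Pearson 95% limits for *x* of *n*: lower = Beta quantile 0.025 with parameters (*x*, *n − x* + 1); upper = Beta quantile 0.975 with parameters (*x* + 1, *n − x*). The lower limit is 0 when *x* = 0.

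| *x*/30 | Rate | 95% CI |
|---|---|---|
| 0 | 0% | 0 to 11.6% |
| 1 | 3.3% | 0.1 to 17.2% |
| 2 | 6.7% | 0.8 to 22.1% |
| 3 | 10.0% | 2.1 to 26.5% |

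- Only AESI is serious: the table shows 0/30; the endpoint is 1/30.
- Three subjects with one AESI each, one of them serious: the table shows 2/30; the endpoint is 3/30.

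These counts are illustrations, not predictions.

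**4. How often it could arise among 90 subjects**

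The documents give no rate of serious AESIs. The nearest figure is in protocol 2.6.1: serious suspected adverse drug reactions of any type in 8 of 7,428 subjects (0.11%). Expected number: 90 × 8/7,428 = 0.10. Chance of at least one: 1 − (1 − 8/7,428)^90 = 9%.

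Serious cardiac events unrelated to vaccine also count as AESIs, and no rate is stated for them. At assumed rates per subject:

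- 0.5%: 1 − 0.995^90 = 36%
- 1%: 1 − 0.99^90 = 60%
- 2%: 1 − 0.98^90 = 84%

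**The case against.** The strongest reply is that nothing is hidden or lost. The rule is stated twice, protocol 9.4.2 leaves analysis details to the SAP, and serious AESIs count towards the primary endpoint. They are listed, tabulated and compared between groups as SAEs, and each SAE is described individually. On this view, assigning each event to one category is a presentation choice, and the endpoint wording does not demand a single combined incidence. All of this is true of the individual events. It does not produce a count of subjects with any AESI, and the AESI outputs are not labelled as covering part of the category.

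Other planned outputs help only in part:

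- Listing 16.2.3.2.3 has no stated inclusion rule and may show serious cases, but it is a listing and gives no incidence.
- Tables 15.3.1.4.1 and 15.3.1.4.2 report unsolicited treatment-emergent events by preferred term, and their titles do not exclude serious ones. They carry no AESI total or flag, and SAP 3.5.9 may leave out events starting after 28 days.
- Table 15.3.2.1 also shows preferred terms, so some cardiac terms could be recognised by eye. Others, such as oedema, stay ambiguous.
- With only a few SAEs, a reader could resolve most of the uncertainty from listings and narratives. That is reconstruction by hand, not a planned result.

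The objection to the upper assumed rates carries weight. Subjects are 18 to 45 years old, those with cardiac history, early family history or a 10-year coronary risk of 10% or more are excluded, and no myocarditis or pericarditis was seen in completed trials of this vaccine. These facts argue against the high end of the range.

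**Conclusion.** The concern holds. Followed exactly, the SAP produces an AESI incidence restricted to non-serious events. That is narrower than the endpoint in both documents, is not labelled as such, and is not declared in SAP 3.6.

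The numerical effect depends on whether a serious AESI occurs. The 9% chance borrows a rate for a different kind of event, and the 36% to 84% range rests entirely on assumed rates, so neither is an estimate for this trial.

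The rule selects on seriousness, and protocol 8.1.2.1 assesses that separately from grade, so severe but non-serious AESIs stay in the table. Protocol Appendix I, however, asks that clinical events judged serious be treated as Grade 4. Where that is applied, the rule also trims the top of the AESI intensity distribution.

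This should be fixed before database lock, but its weight is moderate. The analysis is descriptive, no decision rule uses the figure, and the serious events remain visible as SAEs.

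**What to change.** - In the SAP definition of treatment-emergent AESIs, delete the first sentence and keep the second, which sets the treatment-emergent rule.
- In SAP 3.4.2, delete the sentence that turns a serious AESI into an SAE for reporting.
- Count every AESI in Table 15.3.2.2, in the AESI row of the SAP 3.5.9 overview and in Listing 16.2.3.2.2, with a serious/non-serious split.
- Keep serious AESIs in all SAE outputs, flagged as AESIs.
- Add one sentence stating that the two categories overlap and must not be added.

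The cost is two sentences deleted, one added, one split column and one flag. No new data are needed, because the eCRF already records AESI status by a tick box (protocol 8.3.2).

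If the sponsor prefers to keep the rule, the minimum is to declare it in SAP 3.6 and retitle the outputs as non-serious AESIs. That removes the risk of misreading but still leaves the endpoint unreported as defined.
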